Enrollment and Study Implementation. Study staff will explain the study to veterans and, if interested, the consent form and a one page project description will be mailed. Appointments will then be made for three days of evaluation. Day 1: informed consent; cognitive, psychological and functional screening; Day 2: neuropsychological and self-report measures; and Day 3: cardiopulmonary testing and biological measures. When these evaluations are completed, eligible participants will be scheduled for the first exercise session within two weeks. The exercise training portion of intervention is approximately 24 weeks. After completion of the exercise training, participants will be re-assessed with the cardiopulmonary exercise testing, cognitive measures, biological measures, outcome measures, and measures of physical activity. Participants will then begin four weeks of thrice weekly cognitive training classes at VAPAHCS. At completion of the cognitive training, participants will undergo the post-treatment assessment: cardiopulmonary exercise testing, cognitive measures, biological measures, outcome measures, and measures of physical activity. Participants will receive payments of \$50 for each set of assessments completed.

We plan to telephone screen 200 participants, based upon prior work (Myers et al., 2010; Yesavage et al. 2008), half or 100 are expected to proceed to an in-office evaluation (10 per month), half, or approximately 50 enrolled (5 per month). Dropouts will not be replaced as this is a feasibility study and an aim is to evaluate the appropriateness of the inclusion and exclusion criteria.

All in-house exercise sessions and activity surveillance will be supervised by exercise physiologists certified by the American College of Sports Medicine (ACSM). CT will be taught by the PI.

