CT: All participants will complete a four-week CT course after the six-month exercise phase. The CT will follow the format of a “comprehensive extended” training developed in our earlier work (Fairchild et al., 2010; Yesavage et al., 2008). Training procedures include non-mnemonic “pre-training” combined with mnemonic training. This includes six hours of pre-training in a classroom-type setting (two hours/day) consisting of imagery training, semantic elaboration training, and relaxation training. Once pre-training is complete, all participants com-

plete ten hours of mnemonic training in: 1) list-learning mnemonic and 2) name-face mnemonic. **Method-of-Loci mnemonic**: This mnemonic involves associating a list of words to a fixed list of places (or “loci”).

**Name/face mnemonic**: This mnemonic involves learning faces and names through a three-step technique: 1) choosing a prominent feature of persons face, 2) developing a concrete high imagery transformation of person’s name, and 3) forming a visual image that associates the facial feature with the name. **Design Considerations**: Selection of a single-arm trial was based upon the purpose of the study, which is to establish feasibility of the intervention. Thus a direct comparison group is not needed at this time; however, should this intervention be shown feasible, an active control would be appropriate for inclusion as a direct comparator. A parallel-groups design was chosen so the effect of water-based exercise could be determined separately from that of the CT, thus allowing for preliminary evaluation of water-based exercise alone as an augmentation strategy.

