**Sample size**: One of the proposed project’s aims is to examine recruitment and retention rates for a MCI population in a treatment study. No prior research has examined a water-based physical exercise + CT intervention. To guide power analyses for the current project, studies from both the exercise training and the CT literature were examined. A meta-analysis (Li et al., 2011) of cognitive interventions for persons with MCI reported a modest effect size (0.45). The literature on effect sizes for aerobic interventions for cognitive improvement is more limited and the effects reported are less consistent, hence we assume a small effect size of (0.35), less than that expected for the CT. Using the smaller of the two effect sizes (0.35), we would need 274 participants to test the efficacy of this treatment. In the proposed feasibility study, we will randomize 50 participants over the course of the trial, which we hope will generate more accurate estimates of expected effect sizes as well as demonstrate recruitment feasibility. Ultimately we hope to demonstrate that in a larger RCT over 5 years, recruiting at the same rate, we will be able to recruit the necessary 274 participants.

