### **Database Management and Planned Statistical Analyses**

Data Collection and Database Management. There are three proposed testing time points in this study: prior to randomization (T1), at the end of the exercise program and prior to beginning CT (T2), and at the end of the CT (T3). All identifying information will be removed as data are coded by a unique subject number/identifier. Only the PI and her designee will have access to the identifying information linking subject number to name. All data will be checked for completeness and every effort made to obtain missing data. Data storage will be on computerized password protected databases that are backed up nightly. Additionally, our MIRECC and associated laboratories are familiar with the relevant security and confidentiality issues pertaining to genetic materials and take extra safeguards to protect this information.

Data Analyses. Descriptive analyses of categorical variables will include frequency tables; we will compute measures of central tendency (mean, median, standard deviation, and interquartile range) for those continuous variables. Additionally we will examine the distribution of scores on dependent measures to test assumptions of normality and homogeneity of variance and thus make appropriate transformations when necessary.

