Specific Aim 1: WATER+CT will be feasible as shown by good recruitment and retention rates. Statistical Analyses: To test feasibility of the proposed project, the ratio of enrolled to completed participants will be calculated;  $\geq 80\%$  will be considered good retention. Specific Aim 2: To evaluate the appropriateness of suggested inclusion and exclusion criteria for the aims of the proposed project. Statistical Analyses: We will examine the reported adverse events for participants as well as reasons for screening failures (i.e., those who are consented but excluded from participation prior to randomization). Descriptive analyses of these data will include frequency tables and be used to provide justification for the proposed inclusion and exclusion criteria or to modify them appropriately. Specific Aim 3: To evaluate appropriateness of the WATER+CT for study goals. Statistical Analyses: Appropriateness of treatment conditions will be determined through examination of the participant adherence data. Adherence data will include information from pedometers, heart rate monitors, 7-day activity logs, and cognitive training homework logs. Adequate adherence to exercise prescriptions and CT homework will be defined as completion of  $\geq 80\%$  of assignments as defined by self-report and trainer observation. Specific Aim 4: To assess outcome measurement techniques for participant rate of response in WATER+CT. Statistical Analyses: As this is a single-arm trial, a direct comparison between the WATER + CT condition and a comparative condition is not possible. Participants response rate will be determined by examining the percentage of participants who evidence clinically relevant change after study participation. To determine what a clinically relevant difference in the primary outcome measure (delayed recall of a Word List) would be, we reanalyzed data from our initial clinical trial (Yesavage et al., 2008). Our strategy was to look in that study at the difference in baseline scores between 60 year olds and 70 year olds on the same measure as the proposed work. We found that the difference was 1.7 words. We believe that showing such a difference would be clinically meaningful insofar as it represents a decade of aging's effects on memory. This will be an intent-to-treat analysis, thus all data will be analyzed. Specific Aim 5: To examine outcome "moderator" and "mediator" measurement techniques to determine: a) in whom and under what conditions clinically relevant change occurs and b) the mechanisms through which clinically relevant change occurs. Here we are referring to within subjects effects. Statistical Analyses: Multiple regression modeling will be performed in a preliminary manner to examine individual differences in treatment response depending on baseline (T1) characteristics (age, level of education, APOE and BDNF genotypes). A significant Response Rate X Moderator interaction indicates a differential response rate, e.g., the response rate depends upon age. Such measures are "moderator" variables, i.e., they are used to determine on whom or under what conditions improvement occurs. Additional analyses will be performed to examine the extent to which individual differences in the efficacy of CT treatments depend upon changes in cardiovascular functioning, BDNF plasma levels, and changes in efficiency of working memory (Digit Span) during combined aerobic and resistance exercise training (T1 to T3). These analyses use changes in these two measures as "mediator" variables, i.e., they are used to determine how or why improvement occurs.

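### Beyond general descriptives, the primary outcome is analysed only as a responder percentage, which gives neither the phase-specific change nor the effect-size information the plan wants

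*Combined protocol and SAP*

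**What the plan says.** **The analysis.** Under Specific Aim 4 the plan states: "Participants response rate will be determined by examining the percentage of participants who evidence clinically relevant change after study participation". The yardstick is 1.7 words, the baseline difference between 60- and 70-year-olds in the team's earlier trial. The analysis is labelled intent-to-treat and is to use all data. No start and end visit, interval or treatment of a missing T3 value is given.

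**The general descriptives.** The opening of Data Analyses plans means, medians, SDs and interquartile ranges for continuous variables, and a look at the distributions of the dependent measures. It names no change scores, visits or confidence intervals.

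**The data.** Outcome measures are taken between the two phases. Enrollment and Study Implementation says: "After completion of the exercise training, participants will be re-assessed with the cardiopulmonary exercise testing, cognitive measures, biological measures, outcome measures". Data Collection and Database Management places the second testing point "at the end of the exercise program and prior to beginning CT (T2").

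**The purposes.** Design Considerations says: "A parallel-groups design was chosen so the effect of water-based exercise could be determined separately from that of the CT". A little earlier the same paragraph says: "Selection of a single-arm trial was based upon the purpose of the study". Sample size says of the 50 participants: "which we hope will generate more accurate estimates of expected effect sizes as well as demonstrate recruitment feasibility".

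**Aim 5.** This adds exploratory regressions of treatment response. Its mediators are cardiovascular functioning, plasma BDNF and Digit Span, not word-list recall. Their change is described as occurring during exercise training but is labelled T1 to T3.

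**The concern.** The plan collects three measurements of its primary outcome, one of them exactly at the boundary between exercise and cognitive training (CT), and says it wants to tell the two phases apart. The one analysis it names for that outcome is a single percentage at the end. No T1–T2 or T2–T3 contrast of word-list recall is planned anywhere.

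Dichotomising the change also discards what the larger trial would draw on: how much recall moved, how variable that movement was between people, and how precisely 50 participants estimate it. Followed literally, Aim 4 would deliver a percentage without an interval, over a window chosen later, with an unspecified denominator. The data for a better summary would already be in hand.

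**Working it through.** **Plan figures taken as given.** The 1.7 words cannot be re-derived, because the earlier trial's data are not in the documents. Sample size gives 274 participants for the later trial at an effect size of 0.35, without alpha, sidedness, power or dropout. Two groups, two-sided 5%, 80% power: 2 × (1.960 + 0.842)² / 0.35² = 128.1, so 129 per group and 258 in all (260 with the t distribution). 260 / 0.95 = 273.7, so 274 follows if 5% loss is assumed. It is neither confirmed nor disputed here, and nothing below depends on it.

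**Inputs (Preliminary Work).**
- Earlier CT trial, word-list delayed recall, placebo + CT: mean gain 4.3, SD 4.2. This is a gain to 52 weeks in nondemented adults.
- Ongoing trial in veterans with MCI, delayed recall: 5.83 (SD 2.69) with stretching + CT and 7.25 (SD 4.11) with aerobic/resistance exercise + CT. The test is not named.

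SDs of 2.69 and 4.2 serve as a range and are assumed to apply. Applying 1.7 words to each person's change is an inference, since the text does not say how the yardstick is used.

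**Model.** Change is normal, and a responder gains at least 1.7 words: P = Φ((mean − 1.7) / SD).

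1. *Phases.* The T1–T3 percentage depends only on total change, so by construction it cannot show how the total splits. Mean 4.3, SD 4.2: Φ(2.6 / 4.2) = Φ(0.619) = 73.2%, whether exercise and CT contribute 0 + 4.3, 1.5 + 2.8 or 3.0 + 1.3 words.

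2. *Effect size.* Inverting the model, mean = 1.7 + SD × z(P).

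| Responders | SD 2.69: mean; mean/SD | SD 4.2: mean; mean/SD |
|---|---|---|
| 50% (z = 0) | 1.70; 0.63 | 1.70; 0.40 |
| 70% (z = 0.524) | 3.11; 1.16 | 3.90; 0.93 |

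3. *No mean change.* 1 − Φ(1.7 / 2.69) = 26%; 1 − Φ(1.7 / 4.2) = 34%. Scores are whole words, so the cut-off in effect means two or more. With a continuity correction (1.5 in place of 1.7) the figures are 29% and 36%.

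4. *The MCI gains.* Φ((5.83 − 1.7) / 2.69) = Φ(1.535) = 94%; Φ((7.25 − 1.7) / 4.11) = Φ(1.350) = 91%. The group with the larger mean gain has the lower implied rate, and rates this high leave little room to distinguish anything.

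5. *Do visit-level SDs suffice?* With equal SDs, the SD of change = SD × √(2(1 − r)). For an assumed SD of 4 at each visit it is 4.73, 4.00, 3.10 or 1.79 words at r = 0.3, 0.5, 0.7 or 0.9. The correlation r is not among the planned statistics.

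6. *Precision.* 25/50 has an exact 95% CI of 36% to 64%; none is planned. For a mean change, t × SD / √n gives ±0.76 (SD 2.69) to ±1.19 words (SD 4.2) at n = 50, and ±0.86 to ±1.34 at n = 40. A standardised within-person change of 0.35 would have a 95% CI of 0.06 to 0.63 at n = 50.

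7. *Denominator.* At 80% retention, the plan's threshold for good, an assumed 29 responders are 72.5% of 40 completers but 58% of 50 enrolled.

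**The case against.** Aim 4 concerns response to the combined treatment, and an end-of-study response rate answers that. Phase separation is a design rationale and the effect-size estimate is expressed as a hope; neither is one of the five aims. That is fair and limits the weight of the point. It does not remove the mismatch, because both purposes are stated and nothing else in the plan serves them for word-list recall.

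A reader might infer that the plan reports no mean or SD at all. The documents do not support that. The general descriptives, if tabulated by visit, would give rough phase differences and a rough effect size over the baseline SD. They would not give the SD of within-person change (step 5) or any interval.

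A reader might also infer that Aim 4 excludes T2. The text does not show this: the window is undefined. T1–T3 is the natural reading, not a stated one. Aim 5's reference to change during exercise training hints at phase-specific quantities, but not for word-list recall, and its label runs from T1 to T3.

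The SDs come from other populations or unnamed tests, and the 73% in step 1 uses a 52-week gain in nondemented adults. This stands. The figures illustrate how a percentage behaves; they do not predict this trial's result.

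**Conclusion.** The point holds in limited form. Beyond general descriptives, the only planned analysis of word-list delayed recall is a responder percentage with no defined window, interval or denominator. The plan contains no T1–T2 or T2–T3 change, no SD of change and no CI, though the T2 data are collected. On the assumed SDs and a normal model, the same 50% is compatible with standardised changes of 0.40 to 0.63, and roughly a quarter to a third of participants would count as responders with no mean change.

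It would go too far to conclude that the trial needs a control arm, or that phase-specific changes would supply the effect size for the larger trial. The plan itself acknowledges that a controlled comparison is not possible here. Uncontrolled changes may include time and retest effects, even with counterbalanced alternate lists, and T2–T3 describes CT after exercise, not CT alone. The gain from the fix is a phase-specific description and a change SD.

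Severity is minor to moderate. Aim 4 is descriptive and has no success cut-off, and recruitment and retention under Aim 1 are untouched.

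**What to change.** In Specific Aim 4:

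- Report mean change in word-list delayed recall, with SD and 95% CI, for T1–T2, T2–T3 and T1–T3, using all enrolled participants with available data. A repeated-measures model is one way to do this.
- Set the group mean T1–T3 change and its CI against 1.7 words, since that figure was derived as a difference between groups.
- Keep the responder percentage as a descriptive secondary summary: define it as T1–T3, give a 95% CI, and show it over both enrolled participants and completers.
- State that the changes are uncontrolled, may include time and retest effects, and do not estimate the between-group effect that a larger randomised trial needs.

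In Design Considerations, reconcile the description of the design as parallel-groups with its description as single-arm.

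The cost is SAP wording and a little more analysis, with no new visits or data. The headline may look less favourable than a responder percentage alone. Settling the window and denominators now also prevents their being chosen after the results are seen.

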## **PRELIMINARY WORK**

This work represents a collaborative effort between experts in the field of cognition and exercise training. We are currently conducting a Department of Defense (DOD) funded RCT of the effects of physical exercise and cognitive training in veterans with MCI. Based on our current work, we know that exercise training may augment the effects of CT, thereby increasing its benefit; however it is not known if non-weight bearing exercise, specifically water-based physical exercise, produces a similar effect. Data presented below highlight preliminary work relevant to the proposed project.

Studies Accomplished: Cognitive Training. With over 25 years' experience in CT, we have investigated the efficacy of a pharmacological augmentation strategy for nondemented older adults (Yesavage et al., 2008). This RCT compared two groups: 1) Donepezil + CT and 2) Placebo + CT. The overall results of the trial suggested that Donepezil did not augment the effect of CT as both groups demonstrated improvement from baseline to 52-week follow-up on delayed recall of a word-list (Donepezil + CT group: mean gain score = 4.5, SD = 4.0, p < 0.001; Placebo + CT group: mean gain score = 4.3, SD = 4.2, p < 0.001) and a name-face task (Donepezil + CT group: mean gain score = 1.2, SD = 2.7; Placebo + CT group: mean gain score = 1.6, SD = 2.7).

Studies Accomplished: Exercise Training. [name] has studied and written extensively on exercise training and its benefits for cardiovascular disease patients. Most recently he and his colleagues at VAPAHCs published the results of a randomized prospective longitudinal study of the effects of supervised combined aerobic and resistance exercise training for persons with abdominal aortic aneurysm (Myers et al., 2014). Results indicated that these methods were safe and that participants on average, increased time spent in physical activity to approximately one hour daily of modest exercise which was an improvement of ~30 - 40%. These improvements were notably greater than in similar prior exercise training studies. The authors posited that these marked improvements were partially due to the rigorous activity surveillance and case-managed approach

used in that trial. The proposed project will employ these same methods of surveillance and a case-managed approach, though coupled with water-based physical exercise.

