Ongoing Study: Exercise Training + Cognitive Training. We have successfully collaborated on the current DOD-funded project, "A Combined Training Program for Veterans with Amnestic Mild Cognitive." This project represents the merging of our interests, namely cognitive training and exercise training, towards a new target problem. At completion in September 2015, this ongoing RCT will compare the effects of a combined aerobic and resistance exercise program + cognitive training (CARE + CT) program to a stretching exercise + cognitive training (SE+ CT) program. Interim results indicate that the intervention is relatively well received by participants, as recruitment and retention rates are positive. To date, fifty-five veterans have been randomized to either the CARE+CT or SE+CT condition. Approximately 8% of those randomized have been lost to follow-up. Reasons for discontinuing study participation were largely due to development of acute illness (i.e., CVA or cancer) or injury (i.e., concussion sustained after fall) that prevented further study participation. There are no group-based differential dropout rates. *The preliminary results of this trial suggest that physical exercise does augment the effect of cognitive training as the CARE+CT group, compared to the SE+CT group, demonstrated clinically significant improvements on measures of learning (CARE+CT group: mean gain score = 13.5, SD=11.21; SE+CT group: mean gain score = 9.5, SD=9.68) and delayed recall (CARE+CT group: mean gain score = 7.25, SD=4.11; SE+CT group: mean gain score = 5.83; SD=2.69).*

Over 1500 veterans have been screened study participation and approximately 15% of those were ineligible due solely to musculoskeletal injuries and illnesses (i.e., impaired gait, osteoporosis, degenerative disc and joint disease) that prevent full engagement in weight-bearing exercises. Given the prevalence of these illnesses and injuries in veterans coupled with the increased risk of cognitive impairment, it is vitally important that we investigate methods to extend the cognitive benefit of physical exercise and cognitive training to all

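### Aim 4 judges individual change by 1.7 words, a cross-sectional difference between age groups. Noise and cognitive training alone would produce a high response rate at that cut-off.

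*Combined protocol and SAP*

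**What the plan says.** Under Database Management and Planned Statistical Analyses, Specific Aim 4 states: "Participants response rate will be determined by examining the percentage of participants who evidence clinically relevant change after study participation". The yardstick comes from a reanalysis of the investigators' earlier donepezil and CT trial, which looked at the "difference in baseline scores between 60 year olds and 70 year olds on the same measure as the proposed work". The result is given as "We found that the difference was 1.7 words", and a difference of that size is judged "clinically meaningful insofar as it represents a decade of aging's effects on memory". No other definition of clinically relevant change appears. The plan gives no retest reliability, measurement error, practice allowance, assessment time point or benchmark response rate.

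The same paragraph notes that, in a single-arm study, "a direct comparison between the WATER + CT condition and a comparative condition is not possible". Every participant receives CT after the exercise phase (Research Design, CT). The 16-item word list is described as sensitive to the mnemonics taught (Research Design, Measures). Preliminary Work reports delayed-recall gains in the earlier trial from baseline to week 52, including "Placebo + CT group: mean gain score = 4.3, SD = 4.2". Aim 5 then analyses treatment response against baseline moderators.

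**The concern.** A percentage of responders needs a threshold that separates real change in one person from that person's ordinary test-to-test variation. A difference in baseline scores between people a decade apart in age does not supply one. It may be a difference in group means or a fitted age effect, since the text does not say which. Either way it is a between-person quantity, suited to judging a mean.

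Two consequences follow if it is applied person by person. Some participants who have not changed will count as responders. Many more will count because they had mnemonic training that targets this very task. With no control arm, the rate cannot separate noise, practice and CT from any contribution of water exercise.

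The Specific Aims section says Aim 4 should show whether the measures can determine the efficacy of WATER+CT, and the pilot is meant to prepare a larger trial. A rate of 70% or so could look like support for that trial when CT alone would be expected to give it. The same classification would carry misclassified responders into the Aim 5 analyses.

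**Working it through.** **The plan's figure.** The 1.7 words cannot be reproduced, because no baseline means, SDs or age slope are given. It is taken as stated.

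**Inputs**
- Cut-off c = 1.7 words (Aim 4). The rule of a gain of at least 1.7 is implied, not written out. On whole-word scoring it becomes a gain of 2 or more, approximated by c = 1.5.
- Gains in the earlier trial (Preliminary Work): Placebo + CT mean 4.3, SD 4.2; Donepezil + CT mean 4.5, SD 4.0.
- Assumed, because the documents give no retest SD: SD of change without training of 2 or 1 word.
- Assumed: gains in MCI half as large (mean 2.15, SD 4.2). Background/Significance says only that people with MCI gain less than non-demented adults.

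**Size of the cut-off.** 1.7/4.2 = 0.40 and 1.7/4.0 = 0.42, so about 0.4 SD of individual gains.

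**Share crossing.** With normally distributed change, P(change ≥ c) = 1 − Φ((c − mean)/SD).

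No true change (mean 0):
- SD 4.2: 1 − Φ(0.405) = 34% (36% as 2 or more words)
- SD 2: 1 − Φ(0.85) = 20% (23%)
- SD 1: 1 − Φ(1.70) = 4.5% (6.7%)

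The 34% is an upper figure. The SD of 4.2 was observed after training, so it mixes measurement error with real differences in training response.

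After CT:
- Placebo + CT: 1 − Φ((1.7 − 4.3)/4.2) = 1 − Φ(−0.619) = 73% (75% as 2 or more words)
- Donepezil + CT: 1 − Φ((1.7 − 4.5)/4.0) = 1 − Φ(−0.70) = 76% (77%)
- Gains halved: 1 − Φ((1.7 − 2.15)/4.2) = 1 − Φ(−0.107) = 54% (56%)

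**Precision at this sample size.** If 36 of 50 responded (72%), the exact 95% CI would be 57.5% to 83.8%. That interval includes the 73% expected from CT without exercise.

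**The case against.** The best defence is that this is a descriptive pilot rate. No hypothesis test or target is attached to it; the 80% criteria concern retention and adherence. The plan admits that it has no comparator, says a later trial would need an active control, and looks to the pilot for effect-size estimates, which need not rest on a responder rate. Being unable to isolate exercise is a limit of any single-arm design, whatever the cut-off. T2 comes before CT, so the training argument does not apply there. All of this stands, and it confines the harm to interpretation, planning and Aim 5. It does not justify the cut-off for individuals. Aim 4 refers only to change after study participation, so nothing directs the reader to T2.

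A reader might infer something stronger from the ongoing MCI trial in Preliminary Work: "delayed recall (CARE+CT group: mean gain score = 7.25, SD=4.11; SE+CT group: mean gain score = 5.83; SD=2.69". On the same formula, 94% of the stretching arm and 91% of the active-exercise arm would cross 1.7 words. That suggests the endpoint saturates and ranks the arms in the opposite order to their means. The documents do not support this, for three reasons.

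- The delayed-recall task in that trial is not named. The learning gain reported beside it (mean 13.5, SD 11.21) cannot come from a single 16-item list: gains would lie between −16 and 16, and the largest possible SD is √((16 − 13.5)(13.5 + 16)) = √73.75 ≈ 8.6. The measures listed for the present study include a separate verbal learning test, so the delayed recall may also come from another task.
- On the trial that Aim 4 ties to this word list, 73% to 76% cross. That is high but not a ceiling.
- The arm differences are within sampling error. If all 55 randomised veterans had data, about 27 per arm, the 3-point gap has a standard error of about 7 points, √((0.91 × 0.09 + 0.94 × 0.06)/27). The mean difference of 1.42 words has a standard error of about 0.95, √((4.11² + 2.69²)/27), so z is about 1.5.

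A cut-off of about 6 words, near the stretching arm's mean, fails for the same reasons. It would also make response impossible for anyone starting above 10 of 16.

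**Conclusion.** The point holds in a limited form. The 1.7 words is a between-person difference of about 0.4 SD of individual gains, used without any measurement-error basis to classify individuals. With no true change, the share crossing ranges from 4.5% to 34%, depending on a retest SD that the documents do not give. After CT without active augmentation it is about 73% on the Placebo + CT figures and about 54% if MCI gains are halved. A high rate at T3 is therefore expected without any exercise effect.

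This rests on three assumptions: normal change scores; a rule of gaining at least 1.7 words, which the text implies; and the transfer of week-52 gains in another population to the end of CT here. The documents do not show that nearly everyone would cross, that the rate would rank treatments wrongly, or that the word list itself is a poor outcome. The plan should be changed, although the study remains sound as a feasibility pilot.

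**What to change.** In Aim 4, use 1.7 words as a benchmark for mean change. Report the mean change from T1 with a 95% CI at T2 (after exercise, before CT) and at T3 (after CT). With SD 4.2 the half-width is 1.96 × 4.2/√50 ≈ 1.2 words with all 50 participants and 1.96 × 4.2/√40 ≈ 1.3 words at 80% retention. The T2 change would still include practice and time effects, which should be stated.

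If an individual response rate is kept:
- Base the cut-off on the retest variability of the word-list task (reliable change). For illustration, 1.645 × SD gives 3.3 words at an assumed retest SD of 2 and 4.9 at 3.
- Name the time point.
- Report the rate beside the rate at the same cut-off in the earlier Placebo + CT arm, and in the stretching + CT arm if the same word list was used there. State that these are cross-trial comparisons in different populations.

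In Aim 5, model the continuous change score, not response at 1.7 words.

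The cost is a rewording of Aims 4 and 5 and a short reanalysis of data the investigators already hold. The response rate will probably look less flattering.
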